9.5 Document and data retention

All records pertaining to the conduct of the study, including signed eCRFs, Informed Consent Forms, study product accountability records, source documents, and other study documentation must be retained after study completion according to national legislation and the CTA. Sponsor will inform the sites as to when these documents no longer needs to be retained. Measures should be taken to prevent accidental or premature destruction of these documents (e.g. protection against damage and unauthorised access, preferably by storage in a fire-proof cabinet). Refer to the CTA.

After study completion and database lock, a security sealed CD with electronic study data shall be provided by the eCRF vendor for archiving.

It is the PI's responsibility to inform Q-Med AB in writing if the Investigator file is moved or if the responsibility for the documents is transferred to someone else

10 Statistical Methods

10.1 General

A comprehensive Statistical Analysis Plan (SAP) with detailed description of all statistical analyses will be written and finalized prior to database lock (DBL). All summaries for Group A and B will be done separately. For group A, only descriptive statistics will be used. All statistical analyses, including summary tables and data listings, will be performed using the SAS® system (version 9).

Continuous variables will be summarised using standard statistical measures, such as mean, median, standard deviation, minimum and maximum values. Categorical variables will be presented in frequency tables with number and percent of observations for each level.

CCI

 GALDERMA	Title 43CH1507 Perlane Lido midface study protocol	Doc id MA-30843
--	---	----------------------------------

10.2 Analysis Populations

The following populations will be defined:

- Safety Includes all subjects in Group B who were treated with Perlane-Lido or randomized to no-treatment group. Subjects are analyzed based on the as treated principle.
- Full Analysis Set (FAS) Includes all subjects in Group B who were treated with Perlane-Lido or randomized to no-treatment group. Subjects are analyzed according to the randomisation assignment.
- Per Protocol (PP) Includes all subjects in FAS that comply to the protocol procedures with no deviations that can affect the evaluation of the primary variable.

The FAS population is the primary population for all efficacy analyses. All safety analyses will be based on the Safety population.

10.3 Demographics, baseline assessments, and subject characteristics

[figure not shown]
Demographic endpoints and subject characteristics will be presented by study product using descriptive statistics.

10.4 Efficacy Analysis

Primary analysis

The percent responders (a responder will be defined as a subject with at least 1 grade improvement from baseline MMVS for the right and left sides of the face combined) will be calculated for each treatment group at Month 6 based on the blinded evaluator's assessment. **CCI**

CCI

 GALDERMA	Title 43CH1507 Perlane Lido midface study protocol	Doc id MA-30843
--	---	----------------------------------

CCI

10.5 Safety Analysis

CCI

A

similar summary will also be presented by severity. A graph will be generated to illustrate the incidence over time. Data from the Perlane-L group will be pooled with the no-treatment group.

All AEs will be coded according to MedDRA.

All AEs will be summarised by system organ class (SOC), preferred term (PT) and treatment. Since the no-treatment control group will receive treatment at the month 6 visit, only AEs occurring up until that time point will be included in this presentation, for both groups. Furthermore, all AEs will also be summarised by SOC and PT using the Perlane-L group for the whole study period, and also using the no-treatment group for the study period following their treatment at Month 6.

Related AEs will be summarised by SOC, PT and intensity. In addition, for related AEs the number of days to onset and the duration of event will be summarised by SOC and PT using mean, SD, min, max and median. Action taken for related AEs will also be summarised. Data from the Perlane-L group will be pooled with the no-treatment group.

Serious AEs will be listed.

Non related AEs will be summarised by SOC, PT, and intensity. This will be done as described for all AEs, i.e. based on the following subsets of data: first 6 months following treatment by treatment, the Perlane-L group for the whole study, and the no-treatment group for the period following their treatment.

10.6 Handling of Missing Data

Number of missing values will be summarized and reported as appropriate. The baseline observation carried forward (BOCF) method will be used as the primary method to handle missing data on MMVS up to the Month 6 visit in the FAS analysis set. This strategy is a conservative approach as it treats subjects with missing data as non-responders. Impact of missing data on the primary analysis for Month 6 endpoint will be evaluated by performing sensitivity analysis based on the PP population. In addition, missing data for the primary analysis will also be handled using the multiple imputation method.

All other endpoints will be analyzed on available data, i.e. no imputations will be done.

 GALDERMA	Title 43CH1507 Perlane Lido midface study protocol	Doc id MA-30843
--	---	----------------------------------

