Electronically signed in the document management system within Q-Med quality management system

Clinical Project Manager, Q-Med AB
 PPD

Electronically signed in the document management system within Q-Med quality management system

Study Statistician, Q-Med AB
 PPD

Electronically signed in the document management system within Q-Med quality management system

	Title 43CH1507 Perlane Lido midface study protocol	Doc id MA-30843
--	--	---------------------------

2016-09-07 11:57

Effective date:

Signed Agreement of the Clinical Study Protocol

CTN:

43CH1507

Title of the CSP:

A randomized, multi-center, evaluator-blinded, no-treatment controlled study to evaluate the efficacy and safety of Restylane Perlane Lidocaine for correction of Midface Volume Deficit and/or Midface Contour Deficiency

I, the undersigned, have read and understand the protocol specified above, and agree on the contents. The study protocol, the Clinical Trial Agreement and the additional information given in the Instruction For Use for Restylane Perlane Lidocaine will serve as a basis for co-operation in this study.

Principal Investigator

Printed name

Signature

Date

Study site

Version: 4.0

2016-09-07 11:57

Effective date:

Effective

Version: 4.0

 GALDERMA	Title: 43CH1507 Perlane Lido midface study protocol	Doc id: MA-30843
--	--	-----------------------------------

Synopsis

Title of study:	A randomized, multi-center, evaluator-blinded, no-treatment controlled study to evaluate the efficacy and safety of Restylane Perlane Lidocaine for correction of Midface Volume Deficit and/or Midface Contour Deficiency
Clinical Trial Number:	43CH1507
Countries involved, number of sites/country, number of subjects:	
The study will be conducted at approximately 5 sites in China.
 
Group A: Up to 20 subjects (2 first treated subjects per Treating Investigator) will be enrolled as group A. These subjects will all receive treatment with Restylane Perlane Lidocaine (Perlane-Lido).
 
Group B: Evaluator treatment-blind group with approximately 148 subjects will be randomized in a 3:1 ratio to treatment group or no-treatment control group, i.e., 111 subjects assigned to the Treatment Group and 37 subjects assigned to the Control Group.

Co-ordinating Investigator:	PPD

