1.1.2 Number of subjects and randomization

Approximately 148 subjects will be randomized in a 3:1 ratio to treatment with Restylane Perlane Lidocaine (Perlane-Lido) or to no treatment. The randomization will be stratified by site.

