3.3.2 Handling of missing data

Number of missing values will be summarized and reported as appropriate. The baseline observation carried forward (BOCF) method will be used as the primary imputation method to handle missing data on MMVS up to the Month 6 visit in the FAS analysis set. This strategy is a conservative approach as it treats subjects with missing data as non-responders. Impact of missing data on the primary analysis for Month 6 endpoint will be evaluated by performing sensitivity

	Title Statistical Analysis Plan 43CH1507	Doc id MA-32268
--	---	----------------------------------

Effective date: 2017-04-21 09:20

Effective

Version: 1.0

analysis based on the PP population. In addition, missing data for the primary analysis will also be handled using the multiple imputation (MI) method.

All other endpoints will be analyzed on available data, i.e. no imputations will be done.

If the baseline value is missing, the screening value will be used instead.

Use of MI

The imputation using MI will assume a Missing Completely at Random (MAR) mechanism. The MI procedure of the SAS® system will be used to generate five sets of data with missing values imputed from observed data. It is expected that the pattern of missing data will be monotonic, with slight deviations being corrected by the Markov Chain Monte Carlo (MCMC) method of the MI procedure. Linear regression will be employed to model the missing MMVS score, with the following covariates included in the imputation model: treatment and non-missing data from earlier time points (baseline CCI [REDACTED]). The imputed datasets will be analyzed using the methodology described for the primary analysis of responder rates at Month 6. The results from the analysis of the multiple imputed datasets will be presented as appropriate. The seed number to be used will be 431507 (the clinical trial number of this study, with the letters removed).

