 GALDERMA	Title Statistical Analysis Plan 43CH1507	Doc id MA-32268
---	---	--------------------

Table A 16. MMVS responder rate by treatment and side of the face at Month 6, Blinded Evaluator (FAS)

Assessment/Time Point	Treatment Group	# of Subjects in FAS	# of Responders	Proportion of Responders	95% Confidence Interval	P-Value
Right and Left Midface Combined at Month 6	Perlane-Lido	Xx	Xx	X.XX	X.XX, X.XX	
	Control	Xx	Xx	X.XX	X.XX, X.XX	
	Difference	-	-	X.XX	X.XX, X.XX	X.XX
Right Midface at Month 6	Perlane-Lido	Xx	Xx	X.XX	X.XX, X.XX	
	Control	Xx	Xx	X.XX	X.XX, X.XX	
	Difference	-	-	X.XX	X.XX, X.XX	X.XX
Left Midface at Month 6	Perlane-Lido	Xx	Xx	X.XX	X.XX, X.XX	
	Control	Xx	Xx	X.XX	X.XX, X.XX	
	Difference	-	-	X.XX	X.XX, X.XX	X.XX

Note: Subjects with a missing MMVS have their values imputed using BOCF up to Month 6.

Note: Responder is defined as a subject with an improvement of at least one grade on the MMVS from baseline.

Note: Responder rate is calculated as the number of Responders at the visit of interest divided by the number of subjects in the FAS population for the specific treatment group.

Note: P-values for the difference in proportions are based on the Fisher's Exact test.

Note: 95% Confidence Intervals are two-sided confidence intervals calculated using the exact interval.

Table A 17. MMVS responder rate by treatment and side of the face at Month 6, Blinded Evaluator (PP)

As Table A 16 (only Left and Right Side Combined)

Note: No imputation is used for PP analysis. Only subjects with complete data are included.

Note: Responder is defined as a subject with an improvement of at least one grade on the MMVS from baseline.

Note: Responder rate is calculated as the number of Responders at the visit of interest divided by the number of subjects in the PP population for the specific treatment group.

CCI

 GALDERMA	Title Statistical Analysis Plan 43CH1507	Doc id MA-32268
--	---	----------------------------------

Table A 18. Sensitivity analysis for the MMVS responder rate by treatment and side of the face at Month 6, Blinded Evaluator (FAS)

As Table A 16 (only Left and Right Side Combined)

Note: Missing MMVS values are handled using multiple imputation methods.

Note: Responder is defined as a subject with an improvement of at least one grade on the MMVS from baseline.

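### Five imputations leave avoidable Monte Carlo noise in the multiple-imputation sensitivity analysis of the primary endpoint (SAP Table A 18); a minor point, free to fix

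*Protocol*

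**What the plan says.** Protocol section 10.6 makes BOCF the main way to handle missing scores on the Medicis Midface Volume Scale (MMVS) up to Month 6 in the full analysis set. It adds a per-protocol re-run and then states that "missing data for the primary analysis will also be handled using the multiple imputation method". It gives no number of imputations.

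The number is in SAP section 3.3.2, where the SAS MI procedure "will be used to generate five sets of data with missing values imputed from observed data". The same section states that "Linear regression will be employed to model the missing MMVS score", with treatment and earlier scores as covariates (the list is partly redacted), and that "The seed number to be used will be 431507". It also confirms the ranking of methods: "The baseline observation carried forward (BOCF) method will be used as the primary imputation method".

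The result goes into Table A 18 of SAP Appendix A, whose note reads "Missing MMVS values are handled using multiple imputation methods". The Protocol synopsis gives the arm sizes as "111 subjects assigned to the Treatment Group and 37 subjects assigned to the Control Group".

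**The concern.** The endpoint is binary and the control arm is small: one control responder is 1/37 = 2.7 points of the control rate. In a single imputed dataset, a change in one control's imputed status moves the difference by that amount. Averaged over five datasets, the same change still moves the pooled rate by 2.7/5 = 0.54 points, and several subjects may be missing.

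Table A 18 is there to show how far the handling of missing data moves the primary result. A pooled estimate that would change visibly under another seed serves that purpose less well than it could. This holds even if the imputation model is right and the five results are pooled validly. What is at stake is the numerical precision of a pre-specified sensitivity result, chiefly its confidence limit.

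**Working it through.** **Figure in the plan.** The sample-size rationale is redacted in both documents, so only the split can be checked: 148 × 3/4 = 111 and 148/4 = 37, as stated.

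**Inputs from the documents.** Arm sizes 111 and 37 (Protocol synopsis); m = 5 imputations (SAP 3.3.2); responder rates 88.7% (133/150) and 16.0% (8/50), which are Month 2 results of the earlier US trial (Protocol 2.4.2), used here as planning values.

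**Assumptions.** Missing rate 3% to 20%, equal in both arms; proper binomial imputation within arm; Rubin's rules with a t interval. The visible text gives neither a missing rate nor a pooling rule.

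**Formula.** With the observed data held fixed, the standard deviation (SD) over seeds of the pooled difference is about √(B/m), where B is the between-imputation variance. For an arm of size N with k missing and rate p, its share of B is about

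k·p(1−p)·[1 + k/(N−k)] / N².

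**At 10% missing (4 controls, 11 treated).**
- Control: 4 × 0.16 × 0.84 × (1 + 4/33) / 37² = 0.000440
- Treated: 11 × 0.887 × 0.113 × (1 + 11/100) / 111² = 0.000099
- B = 0.000540 (from unrounded terms)
- m = 5: √(0.000540/5) = 1.04 points
- m = 50: 0.33 points
- m = 100: 0.23 points

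The control arm supplies about four fifths of B.

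**Simulation over seeds, m = 5** (widths cover the central 95% of seeds, in points):

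| Missing | Control + treated missing | SD, difference | Width, difference | Width, lower 95% limit |
|---|---|---|---|---|
| 3% | 1 + 3 | 0.5 | 2.0 | 2.9 |
| 5% | 2 + 6 | 0.7 | 2.9 | 4.4 |
| 10% | 4 + 11 | 1.0 | 3.8 | 6.9 |
| 20% | 7 + 22 | 1.5 | 5.9 | 10.4 |

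The limit moves more than the difference because the seed also changes the estimated between-imputation variance, and so the width of the interval.

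**More imputations, 10% missing.** The lower limit ranges over about 55.9% to 62.9% with m = 5, 58.9% to 60.9% with m = 50, and 59.3% to 60.6% with m = 100. The widths for the difference are about 3.8, 1.2 and 0.9 points. The widths for the limit are about 6.9, 2.0 and 1.4 points.

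**Closer to the SAP's model.** Linear-regression imputation of simulated MMVS scores, by side of the face, at 10% missing and m = 5 gives seed SDs of 0.8 to 1.0 points for the difference and 1.0 to 1.8 for the limit. The effect does not come from the binomial simplification.

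**Shift from BOCF to multiple imputation.** BOCF counts missing subjects as non-responders, so the expected shift in the difference is (k_T/111) × 0.887 − (k_C/37) × 0.16, with k_T and k_C the numbers missing in the treated and control arms:
- 3%: 0.0240 − 0.0043 = 2.0 points
- 5%: 0.0479 − 0.0086 = 3.9 points
- 10%: 0.0879 − 0.0173 = 7.1 points
- 20%: 0.1758 − 0.0303 = 14.6 points

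These are about 4, 6, 7 and 10 times the seed SD.

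**The case against.** The strongest reply is that nothing of consequence depends on this, and most of that reply stands.

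- A reader might infer that agreement or disagreement with BOCF would be chance. The arithmetic does not support this. Read as a deviation, the seed noise is about ±1, ±1.5, ±2 and ±3 points, against expected shifts of 2.0, 3.9, 7.1 and 14.6. Only at 3% missing does the full width come near the shift.
- A reader might infer that the result could be selected by choosing a seed. The SAP fixes the seed in advance, so the result is reproducible and cannot be picked afterwards. A fixed seed does not make it precise, however: it is one draw from the spread shown.
- A reader might infer that the interval rests on 4 degrees of freedom. That number belongs only to the between-imputation component. At 10% missing the within-imputation variance is 0.16 × 0.84/37 + 0.887 × 0.113/111 = 0.00454. Rubin's degrees of freedom are then 4 × [1 + 0.00454/(1.2 × 0.00054)]² ≈ 256. The efficiency of five imputations relative to infinitely many is about 98%, and the seed SD of 1.0 point compares with a sampling standard error of √0.00454 = 6.7 points.
- A reader might infer that superiority is at risk. At these rates, the smallest lower limit over 2,000 seeds with five imputations was about 50 points at 10% missing and 38 at 30%. Only with much weaker assumed rates (60% versus 30%) and at least 20% missing did some seeds put the limit below zero.

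Multiple imputation is also only a supplementary check here: BOCF is primary, and a per-protocol re-run is planned. The figures for the limit depend on Rubin's rules, which the visible text does not name; the relevant notes may be redacted.

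What remains is that the noise exists, is largest in the confidence limit, and can be removed at no cost.

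**Conclusion.** The point holds as a minor one. Five imputations make the lower limit in Table A 18 uncertain by roughly ±3.5 points, and the difference by roughly ±2, at an assumed 10% missing. Both would be smaller with less missing data and larger with more. The noise is not bias, does not affect error control, and does not touch the primary BOCF analysis. The sizes rest on the earlier trial's Month 2 rates, equal missingness in both arms, and Rubin pooling. The missing rate is an assumption throughout, so no single figure can be attributed to the plan itself.

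**What to change.** In SAP section 3.3.2, raise the number of imputed datasets from five to at least 50, for example 100, and keep the stated seed. Optionally, report the Monte Carlo standard error of the pooled difference with Table A 18 so that readers can judge the remaining noise. Protocol section 10.6 needs no change, because it gives no number. At 10% missing, 50 imputations already bring the seed SD of the difference to about 0.3 points and 100 to about 0.2, so the choice between them is a matter of preference. The cost is one number in the SAP and negligible computing time for about 148 subjects.

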10.7 Interim Analysis

No interim analysis is planned.

10.8 Data monitoring committee

Not applicable for this study.

10.9 Withdrawals and deviations

[figure not shown]
All withdrawn subjects will be listed individually, including at least subject number, date and reason for withdrawal, and last visit performed.

Subjects with CSP deviations will be listed individually, including subject number and observed deviation. Depending on the seriousness of the deviation, subject might be excluded from the PP population, which shall be documented prior to DBL.

Deviations from the statistical plan will be documented in protocol Deviation log.

10.10 Sample Size

CCI

11 Protection of personal data

For the purposes of the study, Sponsor will be considered the data controller, and Institution and PI will both be considered data processors.

All processing of personal data must be carried out in accordance with national legislation concerning the protection of personal data. The Institution and the PI are responsible for complying with all requirements pursuant to national legislation in the country in which the Institution and the PI are located. The Sponsor will ensure that all requirements are complied with for data processing, which is carried out in Sweden by the Sponsor.

The Informed Consent Form shall contain information about what personal data to be collected in the study and that this will be kept confidential. The provided information shall

 GALDERMA	Title 43CH1507 Perlane Lido midface study protocol	Doc id MA-30843
--	--	---------------------------

Effective date: 2016-09-07 11:57

Effective

Version: 4.0

be sufficient to enable all subjects to give their consent not only to the participation in the study, but also to the processing of personal data. Such information includes information regarding the purposes of the collecting, processing, data transfer to countries outside China, and the length of time during which personal data will be stored. The subject shall have the right of access to stored personal data, and the right to correction of incorrect information. If a subject decides to terminate the study prematurely, data collected before withdraw of consent will be used in the evaluation of the study, however no new data may be collected. Authorised representatives from the Sponsor or a RA may visit the study site to perform audits/inspections, including source data verification, i.e. comparing data in the subjects' medical records and the eCRF. Data and information shall be handled strictly confidential.

12 Quality Control and Quality Assurance

12.1 Quality control

On-site monitoring of the study will be arranged by the Sponsor according to GCP guidelines to verify that the rights and well-being of the subjects are protected, the reported data are accurate, complete, verifiable from source documents, and that the conduct of the study complies with the approved CSP, subsequent amendment(s), GCP and the applicable regulatory requirements.

Any CSP deviation shall be reported in the eCRF, which shall be verified, discussed, and collected, by the monitor and appropriate corrective and preventive actions shall be taken. The PI is responsible for promptly reporting any deviations from the CSP that affects the rights, safety or well-being of the subject or the scientific integrity of the study, including those which occur under emergency circumstances, to the Sponsor as well as the IEC if required by national regulations. Deviations shall be reviewed to determine the need to amend the CSP or to terminate the study. Handling of CSP deviations shall be performed as described in the monitoring manual.

12.2 Quality assurance

The study site may be subject to quality assurance audit by the Sponsor as well as inspection by appropriate RA. It is important that the PI and other relevant study site personnel are available during the monitoring visits, possible audits, and inspections, and that sufficient time is devoted to the monitoring process.

Each participating member of the study site team shall provide a curriculum vitae (CV) or equivalent that demonstrates their qualifications to conduct the study. The CV shall give name, date and place of birth, address and place of work, and shall show the training, appointments and, for the PI, any other information that confirms the suitability of the PI to be responsible for the study.

It is the responsibility of the PI to ensure that all personnel involved in the study are fully informed of all relevant aspects of the study, including detailed knowledge of and training in all procedures to be followed. All Investigators and other responsible persons shall be listed together with their function in the study on the signature and delegation log.

 GALDERMA	Title 43CH1507 Perlane Lido midface study protocol	Doc id MA-30843
--	--	---------------------------

